12.0 REGULATORY COMPLIANCE, ETHICS, AND REPORTING

12.1 Protection of Human Subjects

12.1.1 Risks to Human Subjects

The proposed project involves human subject's research that is not exempt and involves a randomized clinical trial of a greater than minimal risk intervention to prevent HIV infection. Below we provide sufficient assurance to reviewers that the proposed research meets: (1) the requirements of the DHHS regulations to protect human subjects from research risks (45 CFR Part 46), (2) NIH policy requirements for Data and Safety Monitoring for Clinical Trials, (3) the ClinicalTrials.gov requirements, (4) the requirements of NIH policies on inclusion of women, minorities, and children and (5) the requirements of NIH policy on reporting race and ethnicity data for human subjects in clinical research.

12.1.2 Human Subjects Involvement, Characteristics, and Design

Aim 1 includes examining the impact of iPrEP initiation in the ED by providing a 14-day PrEP “starter pack” and creating linkage with the primary outcome being PrEP usage at 90-days post index visit compared to the linkage only arm, as well as a number of exploratory secondary outcomes including PrEP initiation

and use at 30 and 60 days. We also will collect data on recruitment and attrition rates, as well as means and standard deviations for key measures that will be needed to plan a definitive trial of ED-initiated PrEP.

For Aim 1, we will perform a randomized controlled clinical trial to compare the impact of immediate PrEP initiation (iPrEP) in the ED by providing a PrEP “starter pack” with facilitated linkage alone. The primary outcome is PrEP usage at 90-days post PrEP initiation visit. Participants will provide written informed consent for study participation. The consent to participate will also include 1) consent for investigators to collect prospectively collect clinical and sociodemographic data via medical record review and electronic data capture from the electronic health record. We anticipate 80 patients participating in the study associated with Aim 1.

Study procedures:

Aim 1: 80 PrEP eligible patients will be randomized 1:1 to either the experimental (iPrEP) arm or standard (outpatient PrEP) initiation arm. Patients in the iPrEP arm will receive a 14-day starter pack of PrEP and facilitated linkage. Patient in the control arm will receive facilitated linkage only. Patients in both arms will be followed for 90-days with telephone call follow-up visits scheduled for 30, 60 and 90 days post enrollment. Patients will be asked to complete satisfaction and medication adherence questionnaires at each scheduled follow-up

The setting of the human subjects' will be Mount Sinai Beth Israel Emergency Department.

Subject populations: The study population will include patients recruited in the Emergency Department at Mount Sinai Beth Israel Hospital

Mount Sinai Beth Israel Community Characteristics: The Mount Sinai Beth Israel (MSBI) ED draws patients from a large catchment area that includes the Lower East Side, East Village, Two Bridges, Chinatown and Stuyvesant Town/Peter Cooper Village. The collective population of this geographic region is over 165,000. Included in this region are the following zip codes (10002, 10003, 10004, 10005, 10006, 10007, 10009, 10038). Within this geographic area are some of poorest residents in New York City. In one geographic region within this catchment area, median household incomes were 60% below the NYC mean based on year 2000 census data. Almost 35% of the population were foreign born with 65% of those emigrating from Asia, 26% emigrating from Latin America and 11% from Europe. The catchment area is also home to more than 15 shelters and supportive housing sites, among the highest concentration in NYC. While it is hard to provide exact numbers, there is a large proportion of homeless youth using these support services. It is estimated that 40% of these youth identify as LGBTQ and experience significant exposure to HIV. In regard to access to primary care services, 1 in 4 residents report not having a regular doctor, were currently uninsured, or went without health insurance at some time in the past year. The number of individuals previously tested for HIV is low with only about one fifth of Lower East Side residents having been tested for HIV in the past year. HIV risk factors are high with fewer than 4 in 10 (38%) adults who had more than 1 sex partner in the past year reported using a condom at their last sexual encounter.

Mount Sinai Beth Israel Emergency Department: The MSBI ED has approximately 90,000 annual patient visits. ED demographics are as follows: 51% male, 26% white, 18% African American, 20% Latino, 5% Asian and 31% more than one race. The payer mix is 36% Medicaid, 11% uninsured, 26% Medicare and the remainder with private or other governmental plans.

12.2. Study Procedures, Materials, and Potential Risks

Aim 1

Study Procedures: Patients found to be eligible for PrEP will be randomized to immediate PrEP (iPrEP) initiation using a 14-day starter pack or PrEP initiation in the outpatient clinic. Both groups will have facilitated linkage to care. Follow-up study visits will occur at 30, 60 and 90days post PrEP initiation. The 30, 60 and 90 day assessments will over the phone.

Effective Date: 4/20/2021

End Date: 3/18/2022

Risks: Aim 1 involves randomization to one of two different PrEP initiation programs. PrEP initiation carries risks that would be considered more than minimal. Patients in both groups will be prescribed tenofovir disoproxil fumarate (FTC/TDF) which will be used for women and transgender men or

emtricitabine/tenofovir alafenamide (FTC/TAF) which will be used for men and transgender women. Both of these medications are FDA approved and is being used for its intended purpose in the population for whom it is indicated. Known physical risks of emtricitabine/tenofovir disoproxil fumarate and emtricitabine/tenofovir alafenamide are impaired renal function, intolerable side effects including nausea, vomiting or diarrhea as well as hypersensitivity reaction and osteopenia with long term use. Patients will also be subject to the same psychological and privacy and confidentiality risks.

Sources of Data: Aim 1 data sources will come from the following

- 1) Socio-demographic questionnaires collected during screening and enrollment
- 2) Behavioral risk factor questionnaires collected at enrollment and 30, 60, and 90day follow-up
- 3) PrEP attitude and knowledge measures
- 4) Satisfaction questionnaires collected during enrollment and 30 , 60, and 90-day follow-up
- 5) Laboratory reports obtained from the patient's electronic medical record at enrollment and 30 and 90-day follow-up
- 6) Locator forms collected to obtain correct contact information collected at enrollment and 30 and 60 day follow up
- 7) VSQ-9 study visit questionnaires collected at 30 and 90-day follow-up
- 8) Adherence questionnaires collected at 30, 60, and 90-day follow-up
- 9) Facility follow-up questionnaire

Data for Aim 1 will be collected using a touch screen tablet and paper and pencil surveys administered by the RA. All data will be linked to the individual study participant but will be de-identified for analysis.

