Laboratory abnormalities will be addressed using standard ED clinical protocols. Patient with critical values will be asked to return to the ED for repeat evaluation and laboratory testing. Patients with abnormal values (HBV+ or elevated eCrCl) will be referred for out-patient evaluation. If a patient is found to have a clinical contraindication for PrEP their study participation will end.

Enrolled participants will also be asked to complete a number of validated and study team developed measures including:

- 1) Locator form with additional demographics (Appendix 1)
- 2) Satisfaction questionnaire and qualitative assessment (Appendix 2).
- 3) Attitudes towards PrEP Scale (Appendix 3)
- 4) CDC Sexual Behavior Questions (CSBQ) (Appendix 4)

to ED discharge all patients will receive a referral to an out-patient PrEP provider. Referrals are made through the Institute of Advanced Medicine (IAM) PrEP Warm Line, the IAM REDCap referral system, or via [contact]. Patients will also be asked to sign an Authorization for Release of Medical

Information. The medical release form is needed to confirm clinic follow-up for patients not receiving their follow-up care within the Mount Sinai Health System.

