Patients will be instructed at the time of discharge that they will be contacted by a member of the PrEP Warm Line to schedule follow-up with a PrEP provider. The decision to start PrEP for those not randomized to the iPrEP arm or to stop or continue PrEP for those randomized to the iPrEP arm will be a decision made by the patient in conjunction with their PrEP provider. The ED clinical team will be available to assist patients should have they have any concerns or problems before that linkage occurs. For those randomized to the iPrEP arm if they have any side-effects within the first 14-days of starter pack use they will contact the study team and a decision to continue or stop PrEP will be made after a discussion between the patient and the PI. All patients enrolled in the study will receive standard PrEP counseling which includes information about the need for frequent HIV testing and risk reduction strategies. The importance of follow-up with the PrEP provider will be stressed. We do not anticipate the need for any re-testing (HIV, LFTs, eCrCL) by the study team after ED discharge. These tests are not typically recommended until the patient has been on PrEP for at least 30 days and sometimes not until 90-days. All recommended follow-up testing will be the responsibility of the clinical PrEP provider.

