9.5 Follow-up

All follow-up assessments will be performed over the phone. Follow-up assessments will occur at 30, 60, and 90 days post enrollment.

Follow-up assessments will include:

- 1) Attitudes toward Pre-Exposure Prophylaxis Scale (APS) (Appendix 3)
- 2) Section 4 of ICAP "Screening for Substantial Risk of HIV" (Appendix 5)
- 3) Satisfaction questionnaire and qualitative assessment and visit specific satisfaction instrument (VSQ-9) (Appendix 6)
- 4) Adherence information measured by (1) self-report. Self-report will be assessed with the single measure Guidelines Regimen Information Program (GRIP) guide and questions on last dose and number of missed doses since prior follow-up. (Appendix 7)
- 5) CDC Sexual Behavior Questions (CSBQ) (Appendix 4)
- 6) STAR*D PRISE (Side-effect assessment)

Assessment of engagement in PrEP care at 30, 60, and 90 days post enrollment will be verified by direct contact with the treatment provider/program provided or by EMR review if the patient is linked within the Mount Sinai Health System. If the patient is receiving their PrEP care outside of the Mount Sinai Health System, a signed release authorization form will be sent.

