11.1.2 Analysis of Primary and Secondary Outcomes

Analysis will be on an intention-to-treat basis. In statistical analyses, participants will be included to the date of their last active follow-up visit. Comparisons between control and experimental (iPrEP) arms. To assess the success of randomization, a summary of the baseline variables by treatment group will be tabulated and univariate comparisons performed. The primary outcome, retention in care and PrEP usage, will be compared with proportions and Fisher's exact derived confidence intervals. Secondary outcomes: Secondary analysis will focus on determining how retention in care, risk behavior, adherence or STI diagnosis differ between the groups at any of the follow-up time points. PrEP adherence based on pill counts will be calculated by dividing the number of pills taken by the number of pills prescribed. Adherence will be calculated by study month for each participant. Group adherence comparisons will be compared using Wilcoxon rank sum test. Retention in care, STI diagnosis and risk behavior at each time point will be analyzed for each study visit. Retention in care and STI diagnosis will be treated as dichotomous variables for analysis. Measures of risk behavior will include consistency of condom use and number of sexual partners since prior study visit. Condom use will be treated as an ordinal variable and number of sexual partners as a continuous variable for analysis.

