12.4 Protections against Risk

Investigators will make all efforts to minimize the physical, psychological, privacy and confidentiality risks to human subjects.

Physical Risks: In regard to screening for study entry, patients' discovered to have a clinical/laboratory contraindication for PrEP will be informed and educated by the PI regarding the reason for their ineligibility. Clinical/laboratory abnormalities will be addressed using standard ED protocols. Patients with a primary care provider will be referred back to their doctor for further management. For patients without a primary care provider follow-up will depend on the specific exclusion criteria. Patients with decreased eCrCL will be referred to out-patient nephrology. Patients found to have HBsAg+ will be referred to out-patient Hepatology. Patients found to be HIV+ will be immediately linked to care at Peter Krueger Clinic as per standard ED protocols. Patients found to be pregnant will be referred to out-patient Obstetrics and Gynecology.

All patients initiated on PrEP in the ED will be monitored by the study team for the first 14-days (the duration of the starter pack) or until linked to their outpatient PrEP provider. While we will not be dictating out-patient clinical care we expect that patients will be managed as recommended in the US Public Health Service Pre-Exposure Prophylaxis Clinical Practice Guidelines. This includes repeat HIV testing every 3-months, repeat pregnancy testing for women who may become pregnant, STI testing for sexually active persons with signs or symptoms of infection and eCrCL monitoring (every 6-months).

Psychological Risks: Patients may suffer from anxiety and discomfort at any point during the study. This could be the result of learning that they have one of the medical exclusion criteria or PrEP initiation or a sexually transmitted infection. The RAs will undergo extensive training with the New York City Department of Health and Mental Hygiene (NYC DOHMH) to learn the appropriate counseling skills to address patients concerns. In the event that a RA needs additional assistance they will reach out to the Principle Investigator or social workers from the Emergency Department.

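### Secondary outcomes 5 (STI) and 6 (HIV) rest on tests ordered by PrEP providers who may be outside Mount Sinai, but the plan has no step to collect outside results and no rule for a participant without one

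*Combined protocol and SAP*

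**What the plan says.** Follow-up is remote: "All follow-up assessments will be performed over the phone" (9.5). The study team does not re-test after discharge; section 9.3 states "All recommended follow-up testing will be the responsibility of the clinical PrEP provider". Section 12.2 lists the laboratory source as "Laboratory reports obtained from the patient's electronic medical record at enrollment and 30 and 90-day follow-up".

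That provider may be outside the health system. Section 9.5 verifies engagement in PrEP care by contacting the provider "or by EMR review if the patient is linked within the Mount Sinai Health System", and adds "If the patient is receiving their PrEP care outside of the Mount Sinai Health System, a signed release authorization form will be sent". Section 9.3 gives the purpose of the release: "The medical release form is needed to confirm clinic follow-up for patients not receiving their follow-up care within the Mount Sinai Health System". Section 10.5.2 (Treatment Facility Survey) says the survey confirms where PrEP care is received. The form in Appendix 8 asks about treatment for alcohol use disorder and has no HIV or STI item. Section 10.5.1 (Engagement in Treatment Survey) has services reported by the patient confirmed with the provider or the record; it does not mention diagnoses.

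Section 21.0 defines outcome 5 as the number and type of STIs and outcome 6 as the number of new HIV infections. On analysis, 11.1.2 says "Retention in care and STI diagnosis will be treated as dichotomous variables for analysis", and 11.1.1 rules out imputation of missing data. Neither section says how a participant with no result is classified.

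**The concern.** Both outcomes depend on tests that someone other than the study team orders and records. For a patient in care at Mount Sinai, the chart review should find them. For a patient in care elsewhere, the plan arranges contact with the provider and a signed release, but uses them for attendance and place of care. A test that was done, and that could be requested under a contact already planned, is not requested.

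The study is a pilot meant to supply estimates for a definitive trial (2.1, 4.0, 11.1.3). An STI or HIV rate that depends partly on where care was received, over an unstated denominator, is a poor planning figure. This is separate from who gets tested; it concerns results that exist and are not read.

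**Working it through.** **The plan's own figures.** The only computed design figure is the power table in 11.1.3 for retention and PrEP use with 40 per arm. Exact enumeration of the two-sided pooled Z test reproduces all seven printed powers to four decimals. The table does not concern STI or HIV, for which the plan gives no expected rate.

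**Step 1. Routes by which an outside infection could reach the data.**

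| Route | Where | What it gives for a patient in outside care |
|---|---|---|
| Laboratory reports from the EMR | 12.2 | Probably nothing: 9.5 ties EMR review to patients linked within Mount Sinai, although 12.2 does not state that limit |
| Release and provider contact | 9.3, 9.5 | Follow-up and engagement in care |
| Facility survey | 10.5.2, Appendix 8 | Place of care; no HIV or STI item |
| ICAP Section 4 at each call | 9.5, Appendix 5 | STI yes/no over 6 months; no type |
| CSBQ second tier | 9.5, Appendix 4 | Told of an STD in 12 months, yes/no without type; ever told of HIV |
| HIV as a serious adverse event | 17.2 | HIV acquired while taking PrEP |
| General adverse event questions at each follow-up | 18.1, 18.4 | Whatever the participant reports |

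The STI look-backs of 6 and 12 months are longer than the 90-day follow-up. Recruitment seeks out patients with STI complaints (9.1, 16.0), so a yes at day 30, 60 or 90 can refer to the infection that led to the ED visit. CSBQ is listed at follow-up in 9.5 but at enrollment in 10.4.14, and 9.5 does not name a tier. The first tier folds STI treatment and HIV into one combined yes/no with other risks.

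**Step 2. Size under each possible classification.** Let p be the true proportion diagnosed, s the share whose results lie outside the record, and 40 the number per arm (11.1.3). The documents give neither p nor s, so both are assumed. The formulas also assume that p is the same inside and outside, and that no other route captures the outside diagnoses.

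- If no result counts as negative, the observed rate is p × (1 − s).
- If no result counts as missing, the analysed number per arm is 40 × (1 − s).

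| p | s = 25% | s = 30% | s = 50% |
|---|---|---|---|
| 10% | 7.5% | 7.0% | 5.0% |
| 15% | 11.25% | 10.5% | 7.5% |
| 20% | 15.0% | 14.0% | 10.0% |
| 30% | 22.5% | 21.0% | 15.0% |
| Analysed per arm if missing | 30 | 28 | 20 |

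At p = 15% and s = 30%, the negative reading reports 0.15 × 0.70 = 10.5%, or 4.2 expected diagnoses among 40 instead of 6. The missing reading keeps the rate at 15% on 28 participants, but only if place of care is unrelated to infection.

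**The case against.** A reader might infer that the plan scores outside infections as none. The documents do not say that. Section 11.1.2 only makes STI dichotomous, and entering no for an unseen result sits badly with the no-imputation rule in 11.1.1. Missing is at least as natural a reading. What stands is that the plan does not choose.

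A reader might also infer that outside infections are invisible. They are not. For HIV, everyone is tested at enrollment and a contraindication ends participation (9.3), so a later yes to the CSBQ item on ever being told of HIV would be new. That helps only if the second tier is used at the calls. For STI, the ICAP questions are also asked at screening, so a change from no to yes is visible. But screening precedes the ED tests, so such a change can be the ED infection itself. The enrollment laboratory report would flag those patients without showing whether a second infection followed. Type is still not given.

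A third tempting step is to assume different outside shares by arm and read off a false treatment difference. Section 9.3 gives all patients the same referral routes, and no document gives a share for either arm, so that contrast would be assumption only.

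Finally, section 12.4 expects outpatient management under which "This includes repeat HIV testing every 3-months". A control who links at day 14 would then be tested at about day 14 + 90 = 104, and a reader might infer that the day-90 record review comes too early. That holds only if days run from enrollment, as in 9.5; sections 12.2 and 21.0 count from PrEP initiation. It belongs to that conflict over the time origin, which should be reconciled separately.

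Appendix 9, the release form, was not in the text available to me, so its scope cannot be judged either way.

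**Conclusion.** The point holds as a gap in data collection and in outcome definition. Followed as written, the plan does not request outside HIV or STI results for two listed secondary outcomes, does not name the source that defines them, and does not classify a participant with no retrievable result. Self-report and adverse event questions soften the gap without closing it, above all for STI type and for whether an infection is new.

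The size cannot be fixed from the documents. On the negative reading the observed rate falls in proportion to the outside share; on the missing reading the denominator falls by the same share, and by an amount the plan does not undertake to report. Both rest on the assumptions stated with the formulas, including the reading that the EMR means Mount Sinai's record. No bias between arms is shown. The primary outcome, PrEP usage at 90 days, is unaffected, and these are exploratory outcomes in a pilot. This is a cheap improvement, not a fault that threatens the trial.

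**What to change.** - **Sections 9.5, 10.5.2 (Treatment Facility Survey) with Appendix 8, and 12.2:** add to the existing outside-provider contact a request for the dates, types and results of HIV and STI tests since the ED visit. Check beforehand that the signed release covers laboratory results.
- **Section 11.1.2:** state that a participant for whom no record was obtained from the place of care is missing for these outcomes, not negative. Report the number with records in each arm as the denominator.

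Cost: a slightly longer request to providers already being contacted, one check of the release, and some participants counted as missing. It adds no tests or visits. Collecting the results is the more important half, since the missing rule alone protects the rates only if place of care is unrelated to infection.

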12.3. Adequacy of Protection against Risks

12.3.1 Recruitment & Informed Consent

Participants will be recruited from the MSBI Emergency Department during their ED visit. Participants will be recruited during a single 12-month period. The RA will screen all adult patients using the electronic medical record tracking board. The RA will obtain permission from the clinical team to approach the patient. Using a standardized script, the RA will give a brief description of the study and ask for consent to participate. Patients will be given a consent form that outlines the purpose of the study, length of time of the study, describe what is involved, their responsibilities if they take part in the research, information regarding compensation, potential benefits and foreseeable risks where applicable and study contact information. Potential participants will be asked if they would like time to think about the study and review the consent form. If requested, they will be given as much time as needed to review prior to signing the consent form. In addition to consenting to the survey, patients will also give consent to allow investigators to collect clinical and sociodemographic data from the medical record via chart review and electronic data capture.

The following additional steps will be taken for patient's age 13 to 18. In addition to asking the provider for permission to speak with the patient the study staff will approach the patient and ask them if they are interested in participating in a study about sexual health. If the patient is interested, but is with their adult caretaker the study staff will politely ask as the patient and caretaker if the patient can complete the screening instrument in private. If the patient and caretaker agree the caretaker will be asked to leave the room at which point the study staff will explain the study in more detail and ask the patient if they are willing to participate. If the patient would rather have the caretaker present for the screening and enrollment the study staff will ask to speak with the patient briefly in private to explain that the questions being asked are sensitive and include questions pertaining to sexual activity and drug use. If the patient still would like the caretaker present they will be invited back into the room. If the patient does not want the caretaker to be present they will be asked to wait outside the room until screening and enrollment are complete.

